C2. Study design. Participants will be randomly assigned to SBT or ABBT. Treatment will be delivered in 75-minute, small (12-15 participants), closed-group sessions. Groups will be held weekly in months 1-3, biweekly in months 4-6, and monthly in months 7-12, for a total of 25 sessions. Assessments will occur at months 0 (baseline), 1 (midpoint 1), 3 (midpoint 2), 6 (midpoint 3), 12 (post-treatment), and 24 (1-year follow-up).

C3. Alternative designs considered. While we considered a shorter treatment duration (to reduce burden and increase disseminability), we ultimately chose a 25-session treatment for three reasons. First, 25 sessions over 1 year is about the modal length and the recommended intensity for gold standard weight loss treatment. Second, this length is consistent with the increasingly-supported chronic care model of obesity.¹⁵⁷ Third, clinical trial experts have recommended that, for initial tests of efficacy, treatments should be evaluated at full potency to reduce the likelihood that failure occurs because of sub-optimal dosage.¹⁵⁸ If ABBT improves weight loss outcomes for BED, methods for reducing the intensity (e.g. optimization and refinement of session content) and increasing the scalability (e.g. use of alternative delivery methods and/or non-experts clinicians, both of which have been successfully completed with ABBTs for other disorders¹⁵⁹) can be explored in future studies. We also considered including a second follow-up assessment, but determined that given the time needed to recruit and treat 130 participants with BED, a longer follow-up period would not be feasible.

Timeline	Year 1			Year 2			Year 3			Year 4			Year 5			R = recruitment
Manual refinement	X	X														
Therapist training	X															A = assessment (A ₁ , A ₂ , A ₃ , A ₄ , A ₅ = months 0, 3, 6, 12, 24, respectively).
Wave 1	R	A ₁	A ₂	A ₃		A ₄			A ₅							
Wave 2		R	A ₁	A ₂	A ₃		A ₄			A ₅						
Wave 3			R	A ₁	A ₂	A ₃		A ₄			A ₅					
Wave 4				R	A ₁	A ₂	A ₃		A ₄			A ₅				
Wave 5					R	A ₁	A ₂	A ₃		A ₄			A ₅			
Wave 6						R	A ₁	A ₂	A ₃		A ₄			A ₅		
Data analysis														X	X	
Manuscript preparation														X	X	
Planning future studies, e.g. optimization														X	X	

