Improving Weight Loss Outcomes for Binge Eating Disorder
Statistical Analysis Plan
NCT03712462
March 18, 2024

Statistical Analysis Plan

Statistical analyses were completed using R software version 4.1.3. Data were imputed via two methods to address missingness. Single imputation was used to impute weight measurements using a return-to-baseline approach, with dropouts assumed to have regained 0.15lb per week up to their baseline weight, consistent with assumptions used by other weight loss clinical trials (Wing et al., 2006). Other missing variables were imputed using R “mice” package (Van Buuren & Groothuis-Oudshoorn, 2011). Descriptive statistics were generated for all variables at each assessment point by treatment condition. There were no differences in age, sex, racial or ethnic status, and therapist credentials between treatment conditions.

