Mixed effects models were conducted for Primary Aim 1 (Efficacy of ABT) and Secondary Aim 2 (Between-Subjects Moderation) given nested data within subjects and group. The R “merTools” package was used for models predicting percent weight change and global eating disorder psychopathology change (Knowles et al., 2023), and the R “cplm” package was used for models predicting binge eating frequency change (due to zero-inflated distribution of percent binge eating change at post-treatment and follow-up) (Zhang, 2013). Models for percent weight and binge eating change included fixed effects for the interaction between linear or quadratic time effects and treatment condition (and baseline moderators for Secondary Aim 2). Only linear time effects were included in the models for global eating disorder psychopathology, since the quadratic time fixed effect did not significantly improve model fit. Model selection criteria (e.g., Aikaike information criteria, Bayesian information criteria) and significance testing were used to identify the random effects structure that best fit the model. For percent weight change, models included separate random effects for intercept and slopes of quadratic time effects nested within subjects. For binge eating frequency change, models included random effects for intercept nested within subjects. For global eating disorder psychopathology change, models included separate random effects for intercept and slopes of linear time effects nested within subjects. No differences in results were observed when treatment format delivery (i.e., telehealth vs. in-person groups) was included as a covariate; therefore, results without the inclusion of treatment format delivery as a covariate are reported. Statistically significant interactions were interpreted by plotting simple regression lines for each variable. For all linear mixed effects models, alpha was set at 0.05 and confidence intervals were obtained. Cohen’s f^2 effect size measures were estimated for group x time interaction using methods described by Selya and colleagues (Selya et al., 2012), with $f^2 \geq 0.02$, $f^2 \geq 0.15$, and $f^2 \geq 0.35$ representing small, medium, and large effect sizes, respectively.

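### Both arms are treated in closed therapy groups, but the final models carry only subject-level random effects; if change clusters by therapy group, the standard error of the primary treatment-by-time test is too small

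*SAP*

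**What the plan says.** Protocol section C2 fixes the mode of delivery: "Treatment will be delivered in 75-minute, small (12-15 participants), closed-group sessions". Section C5 plans six recruitment waves. Participants are randomized individually, but the arms follow different manuals (C6a, C6b), so a closed group contains one arm only.

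The SAP explains its use of mixed models as "given nested data within subjects and group". It then says that information criteria and "significance testing were used to identify the random effects structure that best fit the model". The treatment test is the arm-by-time interaction: "Models for percent weight and binge eating change included fixed effects for the interaction between linear or quadratic time effects and treatment condition". For percent weight, the structure finally reported is "For percent weight change, models included separate random effects for intercept and slopes of quadratic time effects nested within subjects". The binge-frequency model has a subject intercept, and the eating-pathology model a subject intercept and linear slope. No level above the subject appears in any of the three.

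The only model check described concerns delivery format: "No differences in results were observed when treatment format delivery (i.e., telehealth vs. in-person groups) was included as a covariate". Protocol section C10 had planned variance components for therapist and for participant within therapist, but none for therapy group. Section C11 counts only the repeated measures on one person as clustering.

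**The concern.** People who meet in the same room for 25 sessions share a leader, peers and group norms, so their weight trajectories may be correlated. Because each group sits inside one arm, group-specific variance in change adds directly to the variance of the difference between arms. A subject-only model treats those people as independent and leaves that variance out. Confidence intervals are then too narrow, and the primary test rejects too often when there is no effect.

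This does not apply to wave effects shared by both arms, to therapist effects balanced across arms (Protocol C8), or in the same way to moderators that vary within groups. A delivery-format covariate does not cure it, since a fixed effect does not account for correlation among members of one group.

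Whether the SAP dealt with the matter is unclear. Its rationale names group as a level of nesting, yet when it says "effect size measures were estimated for group x time interaction", group means treatment arm.

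**Working it through.** **The plan's own figure.** C11 states 104 analysed (52 per arm) for 80% power, and 104/0.8 = 130 enrolled, which reproduces. A plain two-sample calculation at d = 0.46, two-sided 5%, gives 75 per arm. The figure of 52 per arm is reached if baseline covariates explain about 30% of the variance (0.46/√0.70 ≈ 0.55). No such value is given, so 104 is unverifiable rather than wrong. What matters here is that C11 has no therapy-group term.

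**Number of groups.** Six waves × two arms = 12 groups, and 130/12 = 10.8 per group. The stated size of 12–15 would need 12 × 12 = 144 to 12 × 15 = 180 people; at that size, 130 people make 9–10 groups. No layout satisfies both, so 12 groups is taken as the base case and 10 groups of 13 as the variant.

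**(a) Single-outcome approximation.** Design effect = 1 + (m − 1) × ICC; actual alpha = 2 × [1 − Φ(1.96/√design effect)]. Example: m = 10.83 and ICC = 0.05 give 1 + 9.83 × 0.05 = 1.492, a true standard error 1.22 times the reported one, and alpha 0.109. N = 130 is the relevant size because missing weights are filled in: "Single imputation was used to impute weight measurements using a return-to-baseline approach".

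| Assumed ICC | 0.01 | 0.02 | 0.05 | 0.10 |
|---|---|---|---|---|
| 12 groups, N = 130 | 0.061 | 0.073 | 0.109 | 0.164 |
| 12 groups, N = 104 | 0.059 | 0.068 | 0.096 | 0.140 |
| 10 groups, N = 130 | 0.064 | 0.078 | 0.121 | 0.186 |
| 12 groups, N = 130, sampling error adds 50% to slope variance (ICC/1.5) | 0.058 | 0.065 | 0.089 | 0.128 |

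**(b) Longitudinal simulation under the null.** 20,000 runs per setting (Monte Carlo error about 0.002); 130 people in 12 groups; months 1, 3, 6, 12 and 24; subject-only model with quadratic time. Twenty percent drop out and regain 0.15 lb per week up to baseline. Assumed: subject SDs for intercept, linear and quadratic terms of 2, 8 and 4 percentage points (time in years), residual SD 2 or 3, and 230 lb baseline weight. These give an SD of change at month 12 of 6.6–6.9; C11 implies 3.5/0.46 = 7.6. Ranges cover the two residual SDs.

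| Assumed ICC | 0 | 0.01 | 0.02 | 0.05 | 0.10 |
|---|---|---|---|---|---|
| Linear arm-by-time term | 0.053 | 0.056–0.057 | 0.063–0.065 | 0.077–0.085 | 0.097–0.119 |
| Month-12 contrast | 0.052–0.056 | 0.060–0.061 | 0.070–0.071 | 0.099–0.101 | 0.140–0.150 |
| Joint linear + quadratic test | 0.055–0.057 | 0.063–0.064 | 0.072–0.077 | 0.103–0.108 | 0.148–0.172 |

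**(c) Would model selection have caught it?** An F test of group variance at the 5% level, true ICC 0.05, has power 0.287 (12 groups, N = 130), 0.227 (12, 104), 0.306 (10, 130) and 0.244 (10, 104). In a separate simulation of one change score (12 groups of 11, ICC 0.05), a group term was kept by BIC in 12% of trials, by a likelihood-ratio test in 18% and by AIC in 33%. Type I error after selection was 0.08–0.10.

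**(d) Power.** From 80% with no clustering, m = 10.8: 76%, 73%, 63% and 51% at ICC 0.01, 0.02, 0.05 and 0.10 by the normal approximation. A group-level t test on 10 degrees of freedom gives 71% at ICC 0, then 67%, 64%, 54% and 44%.

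**The case against.** The case against is that this is a conditional statement, not a demonstrated error. The documents supply no ICC, no count of groups formed and no analysed N, and the move to some telehealth groups means the realised layout may differ from the 2017 plan. At ICC 0.01–0.02 the error is 6–8%; the larger figures need ICCs for which the documents offer no basis. The simulation inputs are likewise assumed. All of that stands, and it is why ranges are shown.

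Next, the SAP names group as a nesting level and chose its random effects by fit, so a therapy-group term may have been tried and dropped. Nesting within a two-level treatment arm would be an odd reason for a mixed model, so this reading is plausible. But the SAP lists no candidate structures, and with 10–12 groups, dropping the term on fit says little: post-selection error at ICC 0.05 is still 8–10%.

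It is also true that the protocol never promised a therapy-group component, and that an estimated ICC is a result which need not appear in an SAP. The missing therapist component is a separate departure and, with clinicians balanced across arms, is not shown to inflate alpha.

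Finally, the remedy has its own difficulty. In a one-way approximation with 12 groups and N = 130, the estimated group variance is zero in about 55%, 47%, 39% and 22% of trials at ICC 0, 0.01, 0.02 and 0.05. Singular fits are therefore likely, and the fallback must be fixed beforehand. The further power loss at higher ICCs comes from the clustering itself, not from modelling it.

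**Conclusion.** The concern holds as a conditional statement about the primary test. The reported models omit a level of clustering that is nested in arm, and nothing in either document shows it to be negligible. If the ICC for change is near zero, the reported inference stands. At ICC 0.02 the nominal 5% test runs at about 6–8%; at 0.05, at about 8–12%, depending on the contrast and the number of groups. These figures assume 10–12 groups, N = 130, two-sided testing and, for the simulation, the variances listed above. No inflation figure is claimed for the eating-pathology or binge-frequency models. This should be fixed; confidence is medium because the ICC is unknown.

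**What to change.** - For percent weight, fit a version with a therapy-group random effect on change: an intercept and, where estimable, a time slope. Use Satterthwaite or Kenward-Roger degrees of freedom. State in advance that a singular fit leads to a group-level analysis. Present it beside the subject-only model, and do not drop it on AIC, BIC or significance alone.
- Report the number and size of therapy groups by arm and the group ICC. List the random effects tested and dropped, and define what group means in the rationale for mixed models.
- Apply the same check to the eating-pathology and binge-frequency models where they can be fitted.
- State that the 80% power in Protocol C11 assumes no therapy-group clustering, and explain the absent therapist component as a departure from C10.

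The cost is SAP wording and one re-run on data already held, provided group membership was recorded. Intervals will be wider on about 10 cluster degrees of freedom; even at ICC 0 a pure group-level test has 71% power where the plan has 80%. Group and therapist effects may be hard to separate if few therapists led the groups.

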C9. Assessments and Measures. Assessments will occur at the start of treatment (baseline), 1 month (midpoint 1), 3 months (midpoint 2), 6 months (midpoint 3), 12 months (post-treatment), and 24 months (1-year follow up). All outcome and process measures described below will be completed at each assessment. Acceptability will be assessed at post-treatment. All assessments will be completed onsite in Drexel University's Department of Psychology. Efforts will be made to schedule midpoint assessments directly after or directly before a treatment session to reduce participant travel burden (e.g. month 3 assessment will occur between sessions 12 and 13, with effort made to schedule participants right after session 12 or right before session 13 if possible). All assessments will be conducted by blind raters (graduate students who will be highly trained and closely supervised by [name]). Blind raters will receive training on standard procedures for collecting anthropometric data and administering all process measures described below. Raters will be required to pass a "mock" assessment with [name] and reach 100% agreement on eating disorder diagnosis and acceptable reliability (>.80) on EDE scoring before they will be cleared to conduct assessments.

Feasibility and Acceptability. Assessment of feasibility will include number of patients screened per month, % of eligible patients enrolled, treatment attrition (% of patients that prematurely terminate treatment), study retention (% of patients that complete all assessments), treatment adherence, and treatment fidelity. Acceptability will be assessed using the Feedback Questionnaire and Credibility/Expectancy Questionnaire¹⁹⁴ to gauge participant's attitudes and feelings toward the treatment.

Outcomes. The primary outcome measure for the study will be change in **weight**. Weight will be measured in street clothes without shoes using a standardized Secca® scale accurate to 0.1 kg. **Eating pathology** will be a secondary outcome measure and will be measured by The Eating Disorder Examination (EDE), a widely utilized, semi-structured interview for eating disorder symptoms.¹⁹⁵ Participant's EDE global scores and objective binge frequency will be the primary outcome measures for eating disorder pathology.

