Overvaluation of shape and weight will be assessed using the following two questions pulled from the Eating Disorder Examination: “Over the past four weeks, has your shape influenced how you feel about (judge, think, evaluate) yourself as a person?” and “Over the past 4 weeks has your weight influenced how you feel about (judge, think, evaluate) yourself as a person?”. This method of defining and assessing overvaluation of weight/shape has been used in several past studies with BED patients.^{32, 225} Measures used to assess values clarity will be the Valued Living Questionnaire II²²⁶, a commonly used quantitative measure of values, and the Values Clarity Measure, which is an open-ended, qualitative assessment where responses are recorded and coded. The Values Clarity Measure has been proven reliable and valid as a mediator of outcome in a lifestyle modification pilot study conducted by this research team.²²⁷ **Reward sensitivity** will be assessed with the Power of Food Scale, a self-report questionnaire that has been shown to reliably and validly measure thoughts and feelings about highly palatable foods when not physically hungry.^{27, 228, 229}

C10. Statistical Analyses

Descriptive statistics will be generated for all variables. Data summaries will be produced for the combined sample and separately by treatment arm. Continuous variables will be summarized using mean/median as measures of location and SD/inter-quartile range as measures of dispersion; normalizing transformations will be used if there is evidence of skewness/kurtosis. Categorical variables will be presented as proportions.

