Secondary Aim 1 (Between-Subjects Mediation). We will examine the extent to which variables of interest (i.e., dietary restraint, adherence to caloric and physical activity goals, negative affect and distress tolerance, overvaluation of shape/weight, and values clarity) will mediate differences in weight loss and reduction in binge eating between treatments. Specifically, we will determine whether temporally-precedent changes in each mediator from baseline to 1 month and baseline to 3 months mediate subsequent differences in weight loss at 6, 12 and 24 months respectively. We will use the mediation model outlined by Preacher and Hayes and Mplus version 6.12 to estimate the total and specific indirect effects of each hypothesized mediator individually.^{230, 231} This approach expands on Baron and Kenny's methods by providing additional guidelines and techniques that allow for the most robust and accurate interpretation of these mediating effects.^{232, 233} Confidence intervals for the indirect effects will be generated using the bias-corrected (BC) bootstrapping approach.²³⁴

Secondary Aim 2 (Between-Subjects Moderation). Reward sensitivity, overvaluation of shape/weight, negative affect, and distress tolerance will be added to the model described in Aim 1, and allowed to interact with time and treatment arm, to determine whether these variables moderate the effect of treatment.

Statistically significant interactions will be interpreted by plotting simple regression lines for each variable.²³⁵

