For Secondary Aim 1, mediation analyses were conducted using the R “lavaan” structural equation modeling package (Rosseel, 2012). Mediation analyses estimated the indirect effect of treatment condition through change in each mediator from baseline to 3-months on percent change in weight, binge eating frequency change, and global eating disorder psychopathology change at post-treatment and through changes from baseline to 6-months on weight, binge eating frequency change, and global eating disorder psychopathology change at one year follow-up. Baseline levels of the dependent variable and mediator were included as covariates in mediation models. Physical activity minutes and VLQ scores were z-score normalized to correct for significantly larger variances.

References

Knowles, J. E., Frederick, C., Whitworth, A., & Knowles, M. J. E. (2023). Package 'merTools'.

Rosseel, Y. (2012). lavaan: An R package for structural equation modeling. *Journal of statistical software*, 48, 1-36.

Selya, A. S., Rose, J. S., Dierker, L. C., Hedeker, D., & Mermelstein, R. J. (2012). A practical guide to calculating Cohen's f^2 , a measure of local effect size, from PROC MIXED. *Frontiers in Psychology*, 3, 111.

Van Buuren, S., & Groothuis-Oudshoorn, K. (2011). mice: Multivariate imputation by chained equations in R. *Journal of statistical software*, 45, 1-67.

Wing, R. R., Tate, D. F., Gorin, A. A., Raynor, H. A., & Fava, J. L. (2006). A self-regulation program for maintenance of weight loss. *New England Journal of Medicine*, 355(15), 1563-1571.

Zhang, Y. W. (2013). CPLM: compound Poisson linear models. *A vignette for R package cplm*. Available at <http://cran.r-project.org/web/packages/cplm>, 619, 621.

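### Mediation of change in EDE global score by overvaluation may be partly circular, because the mediator is two questions from the same interview

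*SAP*

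**What the plan says.** Four statements, read together, produce the overlap.

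- **Mediator.** Protocol C10, Secondary Aim 1, lists the candidate mediators and ends the list with "overvaluation of shape/weight, and values clarity) will mediate differences in weight loss and reduction in binge eating between treatments". Overvaluation is therefore a named mediator, and the protocol's mediation outcomes are weight loss and binge eating only.
- **Its measure.** Protocol C9: "Overvaluation of shape and weight will be assessed using the following two questions pulled from the Eating Disorder Examination".
- **The eating-pathology outcome.** Protocol C9, Outcomes: "Participant's EDE global scores and objective binge frequency will be the primary outcome measures for eating disorder pathology".
- **The analysis.** The SAP paragraph on Secondary Aim 1 estimates the "indirect effect of treatment condition through change in each mediator from baseline to 3-months" on three outcomes. The third, which the protocol's mediation aim does not have, is "global eating disorder psychopathology change at post-treatment". Mediator change to 6 months is then related to the same outcomes at the next stage, including "global eating disorder psychopathology change at one year follow-up".

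The SAP's only relevant adjustment is this: "Baseline levels of the dependent variable and mediator were included as covariates in mediation models". Neither document mentions the shared items, rescores the outcome or plans a sensitivity analysis without them.

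**The concern.** A mediation model is meant to show that moving one thing moved another. Here the mediator may be a component of the outcome. Suppose treatment lowers the two overvaluation answers at month 3 and they stay lower at month 12. The global score at month 12 is then lower too, simply because it contains those answers. The model reads this as a path from mediator to outcome even if no other symptom changed.

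Baseline adjustment does not address this, because the overlap is between the items at 3 (or 6) months and the same items at 12 (or 24) months. The lag helps only to the extent that the items fail to persist.

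At stake is one interpretive statement: that reducing overvaluation, which is one of the intended targets of the acceptance-based treatment, improved wider eating pathology. As planned, the analysis cannot separate that from persistence of the two answers.

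**Working it through.** The plan gives no figure to reproduce, so the check is to size the artefact.

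**Model.** Write the global score as G = w·O + (1 − w)·R, where O is the two overvaluation items, R is everything else and w is the items' weight. Let φ be the carry-over slope of O from the mediator visit to the outcome visit. Assume overvaluation and treatment have no effect on R, so true mediation of wider pathology is zero. With baseline O and G as covariates, the mediator-to-outcome path is then about w × φ. The spurious indirect effect is about the treatment effect on O times w × φ.

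**Inputs from the documents.** N = 130, and 130 × 0.80 = 104 after the 20% attrition allowed in protocol C11. Alpha is 0.05. The mediator is change from baseline, and the covariates are baseline mediator and baseline outcome, as in the SAP.

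**Inputs assumed (not in the documents).** w from 0.05 to 0.15; φ from 0.4 to 0.8; treatment effect on O of 0.5 to 1 point; SD of O 1.7; SD of R 0.9; baseline correlation of O and R 0.5; later R dependent only on its own baseline. Mediation is declared when both paths are significant at 0.05. This stands in for the interval method, which the SAP does not state.

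**Size of the spurious path and effect.**

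| w | w × φ (φ = 0.4 to 0.8) | Spurious indirect effect, 0.5-point effect, φ = 0.4 | Spurious indirect effect, 1-point effect, φ = 0.8 |
|---|---|---|---|
| 0.05 | 0.020 to 0.040 | 0.5 × 0.020 = 0.010 | 1 × 0.040 = 0.040 |
| 0.08 | 0.032 to 0.064 | 0.5 × 0.032 = 0.016 | 1 × 0.064 = 0.064 |
| 0.15 | 0.060 to 0.120 | 0.5 × 0.060 = 0.030 | 1 × 0.120 = 0.120 |

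Against the assumed SD of 0.9, the middle row is at most 0.064 / 0.9 = 7% of an SD. The bias is small in score points.

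**False-positive mediation (simulated, N = 104 to 130).**

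| w | Items left in the outcome | Items removed |
|---|---|---|
| 0.05 | about 3-14% | about 2-6% |
| 0.08 | about 4-31% (half-point effect 4-15%, 1-point effect 8-31%) | about 2-6% |
| 0.15 | about 9-80% | about 2-6% |

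The rate with items removed can fall below 5% because the test also needs the treatment-to-mediator path to be significant, which often fails with a half-point effect.

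**Second parameterisation.** With O and R given equal SDs, a 0.5 SD treatment effect and φ from 0.3 to 0.7, the rates are about 5-6% at w = 0.05, 5-11% at 0.08, 7-26% at 0.15 and 14-68% at 0.25. With the items removed they are 3.9-5.8%. They are lower at the same w because O then contributes less of the variance of G. The direction and the effect of removing the items agree.

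**Second time point.** The 6-to-24-month model has the same structure over a gap of 18 months rather than 9. If carry-over is weaker over the longer gap, that model sits toward the lower end of each range.

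**The case against.** The strongest objection is that the decisive link is not in the documents. Neither says how the global score is built or that these two items enter it, and the SAP paragraph names neither overvaluation nor the EDE; both come from the protocol. This stands as a limit. Nothing in the SAP replaces the protocol's definitions, and a global score from an interview would naturally include its items. If they are not scored in it, only variance from using the same interview remains.

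Second, the size depends on chosen inputs. That also stands. No single false-positive rate can be defended, and at low weight, weak carry-over or a small treatment effect the inflation is slight.

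Third, improvement in overvaluation is a legitimate part of improvement in global pathology. That is true of the global score as an efficacy outcome. It does not help a claim that one caused the other.

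Two stronger readings are tempting. A reader might infer that the mediation result would be mostly artefact. The documents do not support that: mediator and outcome come from different visits, baseline values are adjusted for, and the null simulated here, in which no other item responds to overvaluation, is an extreme case chosen to isolate the overlap. A reader might also infer that the trial's central mechanism claim is compromised, since protocol B3 puts mechanism testing among its primary goals. But the mediation outcomes in the protocol's own aim share no items with the mediator. The problem is confined to one mediator on one outcome added in the SAP.

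**Conclusion.** The concern holds in limited form. On the condition that the two items count toward the EDE global score, part of any indirect effect through overvaluation on that score is the items predicting themselves, and the planned lag and covariates do not remove it. The spurious path is about item weight times carry-over. Under the stated assumptions, false-positive mediation ranges from close to nominal (3-14% at weight 0.05) through 4-31% at 0.08 to 9-80% at 0.15, against 2-6% once the items are dropped. The width reflects inputs that the documents do not give. The other mediation outcomes, weight and binge frequency, and the primary efficacy result do not depend on this. It is a worthwhile and inexpensive improvement to a secondary analysis.

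**What to change.** State how the EDE global score is computed and whether the two overvaluation questions enter it. If they do, then for the overvaluation mediator only:

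1. Recompute the global score without the two items, at baseline and at follow-up, so that the baseline covariate matches the outcome.
2. Re-run the mediation with that score at both time points: 3-month change to post-treatment, and 6-month change to one-year follow-up.
3. Report it beside the version using the published score.
4. Say that reduced overvaluation improved wider eating pathology only if the item-removed version supports it.

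The cost is one rescored variable and two extra models, with no new data collection. The SAP is written in the past tense, but this can still be done from the interview's item data. The drawback is that the score in this one analysis is non-standard and not directly comparable with published global scores, which is why both versions should be shown.
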